#### D. APPROACH

General Design: This 7-month dietary intervention study will recruit from the Ann Arbor Veterans Affairs Health System and affiliated Community-Based Outpatient Clinics (CBOCs). We hypothesize that dietary modification with the DASH/SRD will improve HF-associated cardiovascular dysfunction in veterans with HTN and metabolic syndrome, and that differential improvements will occur in those with a salt-sensitive BP phenotype vs. those with salt-resistant BP. The study will take place in two phases (Figure 7): Phase 1 participants will consume their usual diet, followed by a DASH/SRD for 14 days each. Salt-sensitive vs. salt-resistant status will be defined by 24-hour BP measurement at the end of each segment In Phase 2, all participants will receive motivational interviewing-based dietary counseling; half will participate in WHEELS-I to promote DASH/SRD adoption over 6 months.

Participants will have a clinical evaluation at 4 time points (denoted by ↑ in *Figure 7* and described below): at weeks 2 and 4 of the *Phase 1* crossover intervention, and at 1 and 6 months of the *Phase 2* DASH/SRD adoption period.

The *Phase 1* primary analysis will evaluate cardiovascular functional changes during usual diet and DASH/SRD diet periods, and test for interaction with saltsensitivity status. Phase 2 will assess the performance of WHEELS-I in promoting DASH/SRD adoption, and evaluate cardiac structural changes between salt-sensitive and salt-resistant

Figure 7: Overall study timeline

Abbreviations: DASH/SRD, sodium-restricted Dietary Approaches to Stop Hypertension; SR, salt-resistant; SS, salt-sensitive; WHEELS-I, Womens' and Men's Hypertension Experiences and Emerging Lifestyles Intervention; **†** = Clinical visit (see text)

participants (as they were defined by BP measurement in *Phase 1*). After completion of *Phase 2*, telephone clinical and mailed dietary questionnaire follow-up will occur after 6 months. An optional, in-person visit may also be performed at this time to obtain arterial tonometry data and clinic blood pressure.

Study Subjects: Veterans aged  $\geq$ 45 years with HTN (here defined as screening systolic BP  $\geq$  130 and/or diastolic BP  $\geq$  85 mmHg, or current use of anti-hypertensive drugs) and metabolic syndrome (body mass index  $\geq$ 30 kg/m² and/or waist circumference >94 cm). These data will be confirmed at study screening. Participants must also be willing to participate in the WHEELS-I program by using a smartphone application or email.

Exclusion criteria: On-treatment, resting systolic BP of >160 mmHg (average of 3 values) at screening visit, previous history of HF, left ventricular ejection fraction <50%, moderate or severe valvular heart disease, myocardial infarction or stroke within the prior 6 months, chronic kidney disease with estimated glomerular filtration rate <45 ml/min/ 1.73m², unoperated aortic aneurysm for which surgery is indicated, prior hyperkalemia requiring urgent treatment, hemoglobin <9 gm/dL, and investigator-determined factors: severe pulmonary disease (e.g. oxygen-requiring) or hepatic disease (e.g. cirrhosis), severely uncontrolled diabetes (hemoglobin A1c >10%), active cancer other than non-melanoma skin or low-risk prostate cancer, other comorbidity with expected survival <12 months, active alcohol/illicit substance abuse, and/or a history of persistent nonadherence to treatment.

Recruitment strategy: Eligible veterans with HTN and metabolic syndrome documented at their most recent clinical encounter will be identified and allocated randomly into blocks of 10. Beginning with the first block, potential subjects will be mailed a letter inviting them to participate in this study. The letter will be followed-up in one week by a telephone call from the study coordinator to discuss the study, pre-screen for eligibility, and schedule the first visit if interested in participation. In order to enroll 110 participants, we plan in-person screening visits for 130 pre-screened veterans who have expressed preliminary interest in the study, (i.e. we anticipate 20 screen-fails). Given staffing, space, and equipment availability, recruitment will take place over 3.5 years with the final in-person clinical study visits (*Figure 1*) in the second quarter of year 4.

Study procedures: will be performed according to the study procedure timeline (*Figure 8*, which includes both phases of the study). All cardiac and vascular measures will be analyzed blinded to dietary assignment, food diary results, 24-hour BP, and urinary electrolytes; 1/10 of cardiovascular studies will be re-analyzed by a second investigator to establish reproducibility and rigor of results. All study data will be recorded in REDCap, a secure research web application, under a unique study ID number assigned to participants.

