- Arterial tonometry: Carotid-femoral pulse wave velocity (cfPWV) will be obtained with a Sphygmocor applanation tonometer (AtCor Medical, Itasca, IL). Pulse waveforms are obtained with gentle tonometer pressure above the carotid and femoral arteries, with cfPWV calculated using the distance between the two sites and the wave transit times, measured using the R wave from simultaneous ECG recording. Radial artery pulse waveforms will also be obtained to measure other parameters of potential interest, e.g. central pulse pressure, aortic augmentation index, and aortic characteristic impedance (Townsend et al. 2015).
- Two- and three-dimensional (3D) echocardiography: B-mode 2D, M-mode, and 3D echocardiographic images will be obtained with the Philips EPIQ 7 ultrasound platform (Philips Electronics, Andover, MA) and recorded via study ID number on DVD and placed under study ID number in the Ann Arbor VA echocardiogram database. Standard cardiac structural, valvular, and functional parameters, including standard measures of diastolic function (e.g., E/A and E/e' ratios), will be measured as per current guidelines. Speckle-tracking of 2- and 4-chamber apical views will be used to obtain global longitudinal strain of the left ventricle using the Philips QLAB program. Parametrized Diastolic Formalism analyses will be performed as described (Chung et al. 2015). 3D images will be used to measure left atrial volume, left ventricular mass, and ejection fraction (Gottdiener et al. 2004, Nagueh et al. 2009, Lang et al. 2015).
- Sublingual sidestream darkfield (SDF) microscopy: Images of the sublingual microcirculation will be obtained and analyzed using an integrated platform that includes a SDF microscope probe and automated software (Glycocheck, Maastricht, Netherlands) (Lee et al. 2014). See *Aim 3* for additional description.

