**Phase 1 study design:** Consented participants will have clinic BP measured at the screening visit and will enter a two-week usual diet period, during which antihypertensive medications, with the exception of calcium channel blockers, will be weaned off under [name] supervision and with guidance from daily home BP monitoring. During this time period, the participant will consume their usual diet. Potential subjects with ontreatment, resting, average systolic BP of > 160 mmHg at the screening visit will be excluded from further

participation, as will those with symptomatic hypertension or systolic BP of > 180 mmHg on more than one occasion during the ad-lib dietary period.

Following the usual diet period and the week 2 visit, participants will consume the DASH/SRD diet for 14 days each. This time period is sufficient to demonstrate changes in BP and arterial stiffness, which peak at 2 weeks after dietary sodium modification (Gates et al. 2004). In addition to in-clinic BP measurement, 24-hour ambulatory BP will be obtained at the end of each dietary sequence. We expect that the DASH/SRD will reduce BP across the cohort, but differentially on an individual basis (Sacks et al. 2001).

The salt-sensitive vs. salt-resistant phenotype will be defined as a change in 24-hour mean BP of ≥8 mmHg between control and DASH/SRD dietary segments (Castiglioni et al. 2011). Based on previous studies in patients with HTN, we expect that 30-50% of participants will be classified as salt-sensitive (Elijovich et al. 2016). The 24-hour ambulatory BP monitoring and 24-hour urinary collections will be used to provide an alternate definition of salt-sensitivity. Specifically, the quantitative Sodium Sensitivity Index will be calculated as the change in 24-hour mean BP divided by the change in 24-hour urinary sodium excretion between DASH/SRD and control diet periods (Castiglioni et al. 2011).

The *Phase 1* primary outcome is the cfPWV compared at the end of usual diet and DASH/SRD. This parameter was chosen because of its association with incident HF in community-dwelling elderly (Tsao et al. 2015) and its high sensitivity and specificity for HF in older adults with unexplained exertional dyspnea (Weber et al. 2013). Key secondary outcomes include ventricular diastolic function (k; ventricular stiffness) and systolic function (global longitudinal ventricular strain) and left atrial reservoir function (left atrial strain).

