Sample size and power: The sample size is based on a combination of logistical considerations and power required to detect important differences in the primary endpoint of change in cfPWV in the context of a randomized crossover design. Sample size is based on a 2-sequence, 2-period, 2-treatment crossover design for continuous endpoints (using paired t test for mean differences). We conservatively assume a within-subject correlation of 0.70 for cfPWV measurements, based on our DASH-DHF pilot (0.81) and literature showing same-day correlation >0.90 (Wimmer et al. 2007) using the Sphygmocor device. We also assume approximate 10% dropout rate during Phase 1 of our study. Under these assumptions and using a two-sided type I error rate of 5%, 100 subjects, 50 allocated to the DASH/SRD-control diet sequence and 50 allocated to the control-DASH/SRD diet sequence, provides >80% power to detect an effect size (mean treatment difference/standard deviation) of 0.22 and >90% power to detect an effect size of 0.26. For comparison purposes, the effect size of cfPWV changes with DASH/SRD in our preliminary work in HFpEF has been 0.4-0.6; in dietary sodium restriction studies in healthier populations than we plan to study, the effect size is at least 0.2-0.4 (Seals et al. 2001, Todd et al. 2010). This sample size provides >80% power to detect an effect size of 0.5 in cfPWV change between salt-sensitive vs. salt-resistant subjects. This is a between-groups comparison based on a two-sample t test and two-sided Type I error of 5%.

Analysis plan: We will examine the distributions of outcomes under each treatment (e.g., DASH/SRD and control diet), as well as by salt-sensitive phenotype. Graphical approaches such as boxplots and scatterplots will be used, allowing identification of outliers, linearity, and correlation of measurements within subject and across time. If the distributional assumptions of our models are not met, transformations will be employed.

Obvious outliers unrelated to data entry error will prompt reconfirmation of acquisition methods and quality by another blinded investigator. We expect no carryover effects due to the two week duration of each dietary segment, a sufficient interval to match sodium intake and excretion even in subjects with chronic kidney disease (McMahon et al. 2013), who have more difficulty achieving this balance.

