[figure not shown]
Dietary Prevention of Heart Failure in Hypertensive Metabolic Syndrome

NCT03170375

May 31, 2025

Statistical Plan

The study was conducted in two phases. *Phase 1* evaluated the salt-sensitivity of blood pressure, with 2 weeks of ad-lib diet followed by 2 weeks of provided sodium-restricted Dietary Approaches to Stop Hypertension (DASH/SRD) meals, with outcomes assessed at 2 and 4 weeks of study participation. *Phase 2* evaluated the efficacy of motivational interviewing-based dietary counseling, with or without the Women's and men's Hypertension Experiences and Emerging LifestyleS (WHEELS) mobile application, with outcomes assessed from baseline to the end of the study. The study schematic is shown below, along with data collection and the flow of participants that were still actively participating at key timepoints.

The primary outcome of *Phase 1* was the change in carotid-femoral pulse wave velocity (PWV), with secondary outcome of the change in left ventricular global longitudinal strain by echocardiography, between week 2 and week 4 of study participation. Since *Phase 1* of the study occurred prior to randomization, the comparator groups are salt-sensitive and non salt-sensitive individuals, with blood pressure salt-sensitivity defined as a reduction in mean arterial pressure by 24-hour ambulatory monitoring in week 4 (DASH/SRD diet period) compared to week 2 (ad-lib diet period). *Phase 1* outcomes were analyzed using linear regression adjusted for baseline value.

Sample size was based on a 2-sequence, 2-period, 2-treatment crossover design for continuous endpoints (using paired t test for mean differences). We assumed a within-subject correlation of 0.70 for PWV measurements, based on our preliminary data and the literature and assumed a 10% dropout rate during *Phase 1* of our study. Under these assumptions and using a two-sided type I error rate of 5%, 100 subjects, 50 allocated to the DASH/SRD-control diet sequence and 50 allocated to the controlDASH/SRD diet sequence, provides >80% power to detect an effect

size (mean treatment difference/standard deviation) of 0.22 and >90% power to detect an effect size of 0.26. This sample size provides >80% power to detect an effect size of 0.5 in cfPWV change between salt-sensitive vs. salt-resistant subjects. This is a between-groups comparison based on a two-sample t test and two-sided Type I error of 5%.

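### In the fixed-order Phase 1, visit, date or read order reveals the diet, and the plan's reader blinding does not mention masking any of them

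*Protocol*

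**What the plan says.** **Blinding.** Protocol section D (Approach), Study procedures: "All cardiac and vascular measures will be analyzed blinded to dietary assignment, food diary results, 24-hour BP, and urinary electrolytes". One in ten cardiovascular studies is re-analysed by a second investigator. The list of masked items does not include visit, acquisition date or reading order.

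**Labelling.** Under the echocardiography procedure, images are "recorded via study ID number on DVD and placed under study ID number in the Ann Arbor VA echocardiogram database". No code for the individual study is described, and nothing is said about how tonometry or SDF files are labelled.

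**Diet order.** Three places give one order for everybody:
- Protocol, General Design: in Phase 1 "participants will consume their usual diet, followed by a DASH/SRD for 14 days each".
- Protocol, Phase 1 study design: "Following the usual diet period and the week 2 visit, participants will consume the DASH/SRD diet for 14 days each".
- SAP: "2 weeks of ad-lib diet followed by 2 weeks of provided sodium-restricted Dietary Approaches to Stop Hypertension (DASH/SRD) meals". The SAP also explains that Phase 1 "of the study occurred prior to randomization, the comparator groups are salt-sensitive and non salt-sensitive individuals".

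**Conflicting text.** The protocol's Phase 1 sample-size paragraph still has "50 allocated to the DASH/SRD-control diet sequence and 50 allocated to the control-DASH/SRD diet sequence". The Phase 1 introduction calls the comparison a two-sequence crossover, and the Phase 1 analysis plan keeps a sequence term. The SAP repeats the two-sequence sample-size basis.

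**The concern.** Withholding the diet label protects a reading only if nothing else the reader sees gives the diet away. In a crossover with randomised order, the visit number carries no information about diet, so withholding the label is enough. With a single fixed order, Week 2 is always usual diet and Week 4 is always DASH/SRD. The visit is then the diet, and masking only the listed items leaves it recoverable from a date or a visit label.

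The protocol's Phase 1 comparison is within person, between the two diet periods, with no concurrent control. A reader who expects DASH/SRD to help could shift Week 4 readings in the favourable direction, and such a shift could not be told apart from a diet effect. The measures most open to this are those a reader traces or fits: k, global longitudinal strain and left atrial strain, all key secondary outcomes of Phase 1. The one-in-ten re-analysis tests reproducibility; it does not remove an expectation shared by two readers who both know the visit.

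**Working it through.** This is a question of design, and no figure in the plan depends on it. The main check sets the texts side by side.

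**Step 1. What does knowing the visit reveal?**

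| Design text | Where | Diet at Week 2 | Does the visit reveal the diet? |
|---|---|---|---|
| Fixed order | Protocol General Design and Phase 1 study design; SAP | Usual diet for all | Yes, fully |
| Two sequences, 50:50 | Protocol Phase 1 introduction, sample size and analysis plan; repeated in the SAP sample-size text | Usual diet for half, DASH/SRD for half | No |

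The blinding sentence is sufficient only in the second row. The schedule and the SAP's account of conduct follow the first.

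**Step 2. Which comparisons are exposed?** Let a reader add a shift b to every Week 4 reading.
- Within-person diet contrast: the expected change becomes (true change + b). It is fully exposed.
- Salt-sensitive versus non-salt-sensitive: (change in one group + b) − (change in the other + b). The b cancels if readers do not know the phenotype. Phenotype comes from 24-hour BP, which is on the masked list. The fallback definition, under the Phase 1 potential problems, uses clinic BP, which is not.
- WHEELS-I versus control: a shift common to both arms at Month 6 cancels in the same way. The arm is randomised, and neither visit nor study ID reveals it.

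**Step 3. Illustration of sensitivity.** The documents give no size for reader bias, and no correlation or detectable effect for k or strain. Only cfPWV has usable inputs, all from the protocol's Phase 1 sample-size paragraph: within-subject correlation 0.70, N = 100, two-sided 5%, paired t test.

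First, the plan's own power:
- SD of the paired difference = √(2 × (1 − 0.70)) = 0.775 SD.
- Effect 0.22: 0.22/0.775 × √100 = 2.84, giving power 80.3%.
- Effect 0.26: 0.26/0.775 × √100 = 3.36, giving power 91.4%.

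Both agree with the stated figures of more than 80% and more than 90%.

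Next, set the true diet effect to zero and add an **assumed** reading shift b between Week 2 and Week 4, with noncentrality b/0.775 × √100:

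| Assumed b (SD) | Noncentrality | Two-sided rejection rate |
|---|---|---|
| 0 | 0 | 5.0% |
| 0.05 | 0.65 | 9.8% |
| 0.10 | 1.29 | 24.8% |
| 0.15 | 1.94 | 48.3% |

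A paired contrast in 100 people is precise enough for a small systematic shift to matter. The table does not say how large the shift is, and it does not transfer directly to the echocardiographic measures.

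**The case against.** The strongest reply is that the protocol commits to blinded analysis, mentions another blinded investigator for checking outliers, and never says that readers see dates, visit labels or order. Silence about method does not show that blinding was absent. This stands. A reader might infer that the blinding did not exist; the documents do not support that, because dates may have been removed and reading order randomised without the plan saying so.

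A reader might also infer that filing echocardiograms under study ID unblinds them. It does not: the ID identifies the participant in coded form, not the visit. It links a participant's studies without hiding their order, and the gap is the missing step on visit and date. That sentence also concerns echocardiograms only.

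Third, cfPWV, the Phase 1 primary outcome, is computed from path distance and ECG-gated transit times, and no offline tracing of it is described. This also stands. Tonometry and SDF are exposed only where files are analysed offline. For the same reason, an assumed shift should not be expressed as a share of the 0.22 SD detectable effect and then applied to strain or k, since 0.22 is a cfPWV figure.

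Fourth, dietary assignment may be meant to cover the WHEELS-I arm, since that randomisation is described under a dietary intervention heading. That is a fair reading; naming the arm would settle it.

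What the reply does not answer is that the masked items, taken as listed, fail to conceal diet under the schedule actually described.

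**Conclusion.** The point holds in limited form. As described, blinding of readers to diet in Phase 1 is not secured: it needs visit, date and read order to be masked, and neither document says that they are. The sentence fits a two-sequence crossover that the fixed-order design does not follow.

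The exposure is the protocol's within-person Week 2 versus Week 4 contrast, chiefly for k, longitudinal strain and left atrial strain. It would go too far to conclude that the SAP's group comparisons are compromised. The salt-sensitivity comparison is largely protected by masked 24-hour BP and the WHEELS-I comparison by randomisation, because a shift common to all readings largely cancels in both. That conclusion assumes readers know neither phenotype nor arm; the clinic-BP fallback is the one route to phenotype that the masking list leaves open.

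The size is unknown. The rise from 5% to about 10%, 25% or 48% for shifts of 0.05, 0.10 or 0.15 SD rests on assumed shifts and on the cfPWV correlation of 0.70 with N = 100. The change is worth making because the remedy is cheap and, with one diet order and no concurrent control, visit-masked reading is the main protection available against reader expectation.

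**What to change.** Amend the Study procedures blinding sentence and the echocardiography labelling text to say that:
- each study, rather than each participant, receives a random code after acquisition, with visit and date removed;
- studies, including the one-in-ten re-reads, are read in random order;
- readers are masked to visit, salt-sensitivity phenotype (including the clinic BP behind the fallback definition) and WHEELS-I arm;
- the same recoding applies to tonometry and SDF files wherever they are analysed offline.

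The SAP is dated May 31, 2025 and written in the past tense, so reading may be finished. In that case, state what was actually masked and limit the blinding claim to it, or re-read the stored echocardiograms under study-level codes.

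Reconcile the crossover wording in the protocol's Phase 1 introduction, sample-size and analysis paragraphs, and in the SAP's sample-size text, with the fixed order.

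Cost: coordinator time for recoding and some delay in reading, with no new procedures. A retrospective re-read would also take reader time. The change covers reading only; the documents do not say who acquires the studies, and recoding cannot mask an operator who is present at the visit.

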### History and exam:

- Clinic BP and heart rate will be measured three times in the seated position and once in the standing position at each visit using an automated sphygmomanometer.
- Standard methods will be used to measure height, weight (all visits), waist and hip circumference (screening and end of study).

Figure 8: Study procedure timeline

		Phase 1		Phase 2		
	Screening	Week 2	Week 4	Month 1	Month 6	Month 6 F/U
History/exam	Х	Х	Х	Х	Х	X (exam optional)
24-hour BP/Urine		Х	Х	Х	Х	
Blood draws	Χ	Х	Х	Χ	Χ	
FFQ	Х				Χ	Х
3-day food diary		Х	Х	Х	Χ	
Arterial tonometry		Х	Х		Χ	X (optional)
Echocardiography		Х	Х		Х	
SDF microscopy		Х	Х		Χ	
Questionnaires		Х			Х	

Abbreviations: BP, blood pressure, FFQ, Food Frequency Questionnaire, SDF, sidestream darkfield microscopy, F/U, follow up

Medical diagnoses,

clinical events (e.g. hospitalizations) and medications will be updated at each visit.

- Questionnaires:
  - Center for Epidemiologic Studies Depression Scale and the 36-item Short Form survey (SF-36) will be
    obtained, as depression and anxiety can affect quality of life and the efficacy of lifestyle change to
    reduce cardiovascular risk factors
  - The SF-36 Physical Functioning Scale and Instrumental Activities of Daily Living. These are planned because functional limitations affect nutrient intake; in turn, changing dietary patterns can affect muscle mass.
  - GOURMET Barriers questionnaire, to assess psychosocial factors related to behavior change.
     Sample attached.
  - Physical Activity Scale for the Elderly (PASE), to assess physical activity level before and after the intervention to ensure outcomes are not attributable to changes in physical activity. Sample attached.
- 24-hour BP measurement: Participants will wear an Oscar II (Suntech Medical Inc, Raleigh, North Carolina) ambulatory BP monitor on the non-dominant arm for 24 hours; BP will be recorded 2 times per hour while awake and 1 time per hour during sleep. Acceptability of recordings for analysis will be assessed according to published international norms (Kikuya et al. 2007).
- Blood tests: *Screening*: comprehensive metabolic panel, complete blood count, B-type natriuretic peptide (BNP), hemoglobin A1C, lipid panel. *All other visits*: basic metabolic panel, insulin, BNP, F2-isoprostanes, aldosterone, IL-6, hs-CRP, TNF-α. These measures were chosen to evaluate the effects of DASH/SRD on renal function, electrolytes, renin-angiotensin-aldosterone system, insulin resistance, and oxidative stress, as well as inflammation markers previously associated with incident HFpEF (Kalogeropoulos et al. 2010). A repeat lipid panel will also be obtained at the end of the study. Whole-blood samples will be used for the mini-SBT (see *Aim 3* for description). Additional samples will be stored for post-hoc biomarker analysis, planned to include syndecan-1 and heparan sulfate, serological markers of endothelial glycocalyx degradation, and the adipokines leptin, adiponectin, and resistin.
- 24-hour urine: All collections: sodium, potassium, creatinine, aldosterone, F2-isoprostanes, and microalbumin. These measures were selected to assess DASH/SRD adherence, the relationship between systemic oxidative stress and renin-angiotensin-aldosterone system activation in salt-sensitive and resistant subjects (Al-Solaiman et al. 2009), and chronic microvascular damage. Additional samples will be

- stored for post-hoc analysis of biomarkers. The completeness of 24-hour urinary collections will be assessed via creatinine excretion per the method of Knuimann et al. (Murakami et al. 2008).
- Dietary assessment: Estimated nutrient intakes from the Block Food Frequency Questionnaire (collected at screening and at the end of study) will be analyzed (NutritionQuest, Berkeley, CA) and scored for DASH/SRD concordance (Mellen et al. 2008). Three-day food diaries will be performed during weeks 2 and 4 of *Phase 1* (i.e., the final week of usual diet and home-delivered DASH/SRD) and at Month 1 and Month 6 of *Phase 2*; these will be initially reviewed for completeness by the study dietitian and analyzed with Nutrition Data System for Research (2015 version; Nutrition Coordinating Center, Minneapolis, MN) through the Michigan Nutrition Obesity Center (MNORC);
- Arterial tonometry: Carotid-femoral pulse wave velocity (cfPWV) will be obtained with a Sphygmocor applanation tonometer (AtCor Medical, Itasca, IL). Pulse waveforms are obtained with gentle tonometer pressure above the carotid and femoral arteries, with cfPWV calculated using the distance between the two sites and the wave transit times, measured using the R wave from simultaneous ECG recording. Radial artery pulse waveforms will also be obtained to measure other parameters of potential interest, e.g. central pulse pressure, aortic augmentation index, and aortic characteristic impedance (Townsend et al. 2015).
- Two- and three-dimensional (3D) echocardiography: B-mode 2D, M-mode, and 3D echocardiographic images will be obtained with the Philips EPIQ 7 ultrasound platform (Philips Electronics, Andover, MA) and recorded via study ID number on DVD and placed under study ID number in the Ann Arbor VA echocardiogram database. Standard cardiac structural, valvular, and functional parameters, including standard measures of diastolic function (e.g., E/A and E/e' ratios), will be measured as per current guidelines. Speckle-tracking of 2- and 4-chamber apical views will be used to obtain global longitudinal strain of the left ventricle using the Philips QLAB program. Parametrized Diastolic Formalism analyses will be performed as described (Chung et al. 2015). 3D images will be used to measure left atrial volume, left ventricular mass, and ejection fraction (Gottdiener et al. 2004, Nagueh et al. 2009, Lang et al. 2015).
- Sublingual sidestream darkfield (SDF) microscopy: Images of the sublingual microcirculation will be obtained and analyzed using an integrated platform that includes a SDF microscope probe and automated software (Glycocheck, Maastricht, Netherlands) (Lee et al. 2014). See *Aim 3* for additional description.
- Safety Monitoring: Patients will perform home BP monitoring with their own personal cuff or a provided Omron 7 series automated cuff (Omron Healthcare, Lake Forest, IL). Monitoring will be daily during the run-in period and *Phase 1* of the study, and at least weekly thereafter if systolic BP is >180 or <100 mmHg on more than one occasion, or if symptoms suggest hyper- or hypovolemia (e.g., worsening/new edema, dizziness), the participant will be scheduled for an in-person safety visit. Targeted history and physical will be performed by a clinician-investigator, with laboratory or other testing obtained based on the clinical presentation. Antihypertensive medications may be adjusted at this visit if needed for participant safety. Safety visits may also be scheduled for worsening glycemic control in diabetic participants. See *Human Subjects Protection* section for additional details.

Study phase 1: Phenotype veterans with HTN and metabolic syndrome as salt-sensitive or salt-resistant; determine effects of a 2-week DASH/SRD intervention vs. control diet on HFpEF functional cardiovascular risk factors in salt sensitive compared to salt-resistant veterans.

Introduction: Animal models, cohort studies, and our preliminary work suggest that the DASH/SRD would favorably affect cardiovascular parameters that predict incident HFpEF in veterans with HTN and metabolic syndrome, and have a stronger effect in salt-sensitive individuals. Our working hypothesis is that the DASH/SRD will produce significantly greater improvement than control diet in HFpEF risk factors including large-arterial stiffness (carotid-femoral pulse wave velocity [cfPWV], primary outcome), left ventricular diastolic function, and left ventricular systolic function. We further hypothesize that the improvement in these measures will be greater in salt-sensitive veterans. We will test our hypotheses in a 2-sequence, 2-period, 2-treatment comparison of DASH/SRD vs. control diet.

**Phase 1 study design:** Consented participants will have clinic BP measured at the screening visit and will enter a two-week usual diet period, during which antihypertensive medications, with the exception of calcium channel blockers, will be weaned off under [name] supervision and with guidance from daily home BP monitoring. During this time period, the participant will consume their usual diet. Potential subjects with ontreatment, resting, average systolic BP of > 160 mmHg at the screening visit will be excluded from further

participation, as will those with symptomatic hypertension or systolic BP of > 180 mmHg on more than one occasion during the ad-lib dietary period.

Following the usual diet period and the week 2 visit, participants will consume the DASH/SRD diet for 14 days each. This time period is sufficient to demonstrate changes in BP and arterial stiffness, which peak at 2 weeks after dietary sodium modification (Gates et al. 2004). In addition to in-clinic BP measurement, 24-hour ambulatory BP will be obtained at the end of each dietary sequence. We expect that the DASH/SRD will reduce BP across the cohort, but differentially on an individual basis (Sacks et al. 2001).

The salt-sensitive vs. salt-resistant phenotype will be defined as a change in 24-hour mean BP of ≥8 mmHg between control and DASH/SRD dietary segments (Castiglioni et al. 2011). Based on previous studies in patients with HTN, we expect that 30-50% of participants will be classified as salt-sensitive (Elijovich et al. 2016). The 24-hour ambulatory BP monitoring and 24-hour urinary collections will be used to provide an alternate definition of salt-sensitivity. Specifically, the quantitative Sodium Sensitivity Index will be calculated as the change in 24-hour mean BP divided by the change in 24-hour urinary sodium excretion between DASH/SRD and control diet periods (Castiglioni et al. 2011).

The *Phase 1* primary outcome is the cfPWV compared at the end of usual diet and DASH/SRD. This parameter was chosen because of its association with incident HF in community-dwelling elderly (Tsao et al. 2015) and its high sensitivity and specificity for HF in older adults with unexplained exertional dyspnea (Weber et al. 2013). Key secondary outcomes include ventricular diastolic function (k; ventricular stiffness) and systolic function (global longitudinal ventricular strain) and left atrial reservoir function (left atrial strain).

Dietary intervention: At the week 2 visit, a printed guide to the DASH/SRD produced by the U.S. Department of Health and Human Services will be provided, and participants will complete a standardized questionnaire that establishes their cognitive representation of the DASH/SRD (Scisney-Matlock et al. 2006). Baseline nutrient intake will be assessed with the Block Food Frequency Questionnaire and Nutrition Quest software (NutritionQuest, Berkeley, CA). This instrument has previously been used to assess DASH/SRD concordance (Mellen et al. 2008). Following this visit, participants will consume 14 days of DASH/SRD provided meals, designed by [name]. These will be prepared, pre-packaged, and home-delivered twice weekly by PurFoods, LLC. The study DASH/SRD sodium content will be 50 mmol (1,150 mg/2,100 kcal), as used in the DASH-Sodium study (Sacks et al. 2001). Both diets will be calorie-adjusted to maintain stable body weight using the National Institutes of Health body weight planner (Hall et al. 2011). Nutrient consumption during *Phase 1* will be assessed by 3-day food diary during the second week of each dietary period; results will be corroborated by 24-hour urinary sodium and potassium.

Sample size and power: The sample size is based on a combination of logistical considerations and power required to detect important differences in the primary endpoint of change in cfPWV in the context of a randomized crossover design. Sample size is based on a 2-sequence, 2-period, 2-treatment crossover design for continuous endpoints (using paired t test for mean differences). We conservatively assume a within-subject correlation of 0.70 for cfPWV measurements, based on our DASH-DHF pilot (0.81) and literature showing same-day correlation >0.90 (Wimmer et al. 2007) using the Sphygmocor device. We also assume approximate 10% dropout rate during Phase 1 of our study. Under these assumptions and using a two-sided type I error rate of 5%, 100 subjects, 50 allocated to the DASH/SRD-control diet sequence and 50 allocated to the control-DASH/SRD diet sequence, provides >80% power to detect an effect size (mean treatment difference/standard deviation) of 0.22 and >90% power to detect an effect size of 0.26. For comparison purposes, the effect size of cfPWV changes with DASH/SRD in our preliminary work in HFpEF has been 0.4-0.6; in dietary sodium restriction studies in healthier populations than we plan to study, the effect size is at least 0.2-0.4 (Seals et al. 2001, Todd et al. 2010). This sample size provides >80% power to detect an effect size of 0.5 in cfPWV change between salt-sensitive vs. salt-resistant subjects. This is a between-groups comparison based on a two-sample t test and two-sided Type I error of 5%.

Analysis plan: We will examine the distributions of outcomes under each treatment (e.g., DASH/SRD and control diet), as well as by salt-sensitive phenotype. Graphical approaches such as boxplots and scatterplots will be used, allowing identification of outliers, linearity, and correlation of measurements within subject and across time. If the distributional assumptions of our models are not met, transformations will be employed.

Obvious outliers unrelated to data entry error will prompt reconfirmation of acquisition methods and quality by another blinded investigator. We expect no carryover effects due to the two week duration of each dietary segment, a sufficient interval to match sodium intake and excretion even in subjects with chronic kidney disease (McMahon et al. 2013), who have more difficulty achieving this balance.

An intention-to-treat approach will be used to analyze endpoints, including all randomized participants. Multiple imputation will be used for missing data, which assumes that outcome data are missing at random (i.e., where other variables from the study can account for differences in the primary outcome for observed and missing subjects) (Little et al. 2012). A linear mixed effects model (Verbeke et al. 2000, Diggle et al. 2013) will be used to assess the effect of intervention on the change in cfPWV, with fixed-effect terms for sequence, study period, dietary intervention, and adjusting for baseline cfPWV and other potential confounders, e.g. age, race, body mass index, diabetes status, and renal function. A random-effect term will be included to account for the correlated measurements for each subject. Tests to compare diet will be based on Wald and chi-squared tests based on maximum likelihood or restricted maximum likelihood methods. Alternative covariance structures (other than compound symmetry) will be explored and model fit will be examined using the Akaike Information Criteria (Holford 2004). This approach will also be used for the key secondary endpoints (ventricular diastolic stiffness k and global longitudinal ventricular strain) and other cardiovascular parameters (e.g. E/e' ratio). For binary secondary outcomes (e.g. serious adverse events) a similar mixed model approach will be employed (Ezzet et al. 1992). To test whether improvements in the primary and key secondary endpoints are greater in salt-sensitive than in salt-resistant subjects, interaction will be assessed via the linear mixed model described above, with a fixed-effect term for salt-sensitivity phenotype.

